IMV duration in survivors (Secondary Outcome)	Time from start of index intubation to successful liberation. Successful liberation is defined as no death or re-intubation within 24 hours of extubation.	
Patients who are intubated past 90 days of index intubation are imputed as 90 days.
 
Patients who die within 24 hours of extubation are excluded.
	Log transformed multiple linear regression controlling for blocking variables and confounders.	
IMV duration will be expressed in days.
 
Adjusted mean difference and 95% C.I. for REDvent vs. usual care will be back transformed with $\exp(\text{estimate})$ and interpreted as a relative change.
	None

Received NIV after extubation (secondary outcome)	Yes/no binary variable for receiving oro-mask CPAP or Bi-level ventilation after successful extubation. Successful extubation is defined as no death or re-intubation within 24 hours of extubation.	Patients who die within 24 hours of IMV or remain on IMV at 90 days are not included.	Multivariable logistic regression controlling for blocking variables and confounders.	Adjusted odds ratio for receiving NIV post-extubation with 95% C.I. for REDvent vs. Usual care will be presented.	January 2024 added as necessary component to interpret length of NIV after extubation more appropriately.
NIV duration after extubation (secondary outcome)	Duration of non-invasive ventilation after extubation is defined as the number of days and hours that the patient is on oro-mask CPAP or Bi-level ventilation after successful extubation. Successful extubation is defined as no death or re-intubation within 24 hours of extubation.	Patients who die within 24 hours of IMV or who never receive NIV post-extubation are excluded. Patients who remain on NIV at 90 days will have 90 days imputed. Patients who die while on NIV will have their death date as end of NIV duration	Log transformed multiple linear regression controlling for blocking variables and confounders.	NIV duration will be expressed in days. Adjusted mean difference and 95% C.I. for REDvent vs. usual care will be back transformed with exp(estimate) and interpreted as a relative change.	None

Received Non-invasive respiratory support (NRS) post-extubation (secondary outcome)	Yes/no binary variable for receiving NRS after successful extubation. NRS includes: High Flow Nasal Cannula (HFNC) or nasal-only modes of non-invasive ventilation (CPAP or Nasal IMV or BiPAP) Successful extubation is defined as no death or re-intubation within 24 hours of extubation.	Patients who die within 24 hours of IMV or remain on IMV at 90 days are not included.	Multivariable logistic regression controlling for blocking variables and confounders.	Adjusted odds ratio for receiving NRS post-extubation with 95% C.I. for REDvent vs. Usual care will be presented.	January 2024 added as necessary component to interpret length of NRS after extubation more appropriately.
NRS duration after extubation (secondary outcome)	Duration of NRS after extubation is defined as the number of days and hours that the patient is on NRS after successful liberation. End of NRS is defined as absent continuously for at least 24 hours. Successful extubation is defined as no death or re-intubation within 24 hours of extubation.	Patients who die within 24 hours of IMV or who never receive NRS post-extubation are excluded. Patients who remain on NRS at 90 days will have 90 days imputed. Patients who die while on NRS will have their death date as end of NIV duration.	Log transformed multiple linear regression controlling for blocking variables and confounders.	NRS duration will be expressed in days. Adjusted mean difference and 95% C.I. for REDvent vs. usual care will be back transformed with $\exp(\text{estimate})$ and interpreted as a relative change.	None
Re-intubation within 48 hours of extubation (secondary outcome)	Binary variable for re-insertion of endotracheal tube within 48 hours of initial extubation.	Patients who remain on IMV for their index intubation or die within 48 hours of index extubation are excluded.	Multivariable logistic regression for the event re-intubation = yes. Adjusting for blocking variables and confounders.	Binary yes/no variable. Adjusted odds ratio for re-intubation with 95% C.I. for REDvent vs. Usual care will be presented.	None

28-day ventilator free days (secondary outcome)	Number of days between index intubation and 28-days post-index intubation in which patient is alive and not on IMV.	No exclusions.	Competing risks regression adjusting for blocking variables and confounders. Censoring indicators: 0=those who do not die but are not extubated within 28 days 1=those that have successful liberation within 28-days 2=those that die within 28-days	If patient is re-intubated within 24 hours of extubation the time in between intubations is not counted towards VFDs. If a patient is extubated for >24 hours and then subsequently re-intubated they get credit for those days without IMV. Values are 0 to 28 days. Adjusted hazard ratio and 95% C.I. will be presented.	January 2023- Updated competing risk regression to negative binomial model to align with analysis plan for primary outcome and because the variable is a count of the number of days. Negative binomial also treats death and those on IMV for 28 days as the same (zero VFDs). This aligns with the hypothesis that the influence of the treatment variable is on the days of ventilation, and we do not expect any treatment effect for death.
PiMax on day of 1st SBT (secondary outcome)	PiMax value on the day the 1 st SBT was performed.	Patient with values >100 will be truncated to 100. Exclude patients who never attempted an SBT in the 28-days study period.	Multiple linear regression adjusting for blocking variables and confounders.	Adjusted mean difference with 95% C.I. will be presented for REDvent vs. Usual care.	June 2024- unable to satisfy assumptions of linear regression with any transformation. Modeled as non-parametric proportional odds logistic regression.

PiMax on day of extubation (secondary outcome)	PiMax value on the day of extubation. Restricted to those who met primary outcome (SBT passage or successful extubation).	Patient with values >100 will be truncated to 100. Exclude patients who died within 24 hours of extubation or remained intubated at 90 days.	Multiple linear regression adjusting for blocking variables and confounders.	Adjusted mean difference with 95% C.I. will be presented for REDvent vs. Usual care.	June 2024- unable to satisfy assumptions of linear regression with any transformation. Modeled as non-parametric proportional odds logistic regression.
ICU mortality (secondary outcome)	Yes/no binary variable for did patient die in the ICU.	No exclusions	Multivariable logistic regression controlling for blocking variables and confounders.	Adjusted odds ratios for death in REDvent vs. Usual care with 95% C.I. will be presented	None
90-day mortality (secondary outcome)	Yes/no binary variable for did patient die in the hospital and within 90 days.	No exclusions	Multivariable logistic regression controlling for blocking variables and confounders.	Adjusted odds ratios for death in REDvent vs. Usual care with 95% C.I. will be presented.	None
Time to 1st SBT (secondary outcome)	Number of days from start of index intubation to either first SBT or successful extubation, whichever came first. Successful extubation defined as no death or re-intubation within 24 hours of extubation.	Patients who never received an SBT and were successfully extubated after 31 days (time from start of IMV to end of protocol) were truncated to 31 days.	Log transformed multiple linear regression controlling for blocking variables and confounders.	Time will be expressed in days. Adjusted mean difference and 95% C.I. for REDvent vs. usual care will be back transformed with exp(estimate) and interpreted as a relative change.	None
Time to 1st SBT passage (secondary outcome)	Number of days from start of index intubation to either first SBT passage or successful extubation, whichever came first. Successful extubation defined as no death or re-intubation within 24 hours of extubation.	Patients who never passed an SBT and were successfully extubated after 31 days (time from start of IMV to end of protocol) were truncated to 31 days.	Log transformed multiple linear regression controlling for blocking variables and confounders.	Time will be expressed in days. Adjusted mean difference and 95% C.I. for REDvent vs. usual care will be back transformed with exp(estimate) and interpreted as a relative change.	None

Decline in PCPC from baseline to ICU discharge	Change in PCPC defined as baseline minus ICU discharge value. This change was dichotomized into a change of ≥ 0 (no change or increased) vs. change of <0 (decline in PCPC).	Patients who did not survive to ICU discharge were excluded.	Multiple logistic regression controlling for blocking variables and confounders.	Adjusted odds ratio for the outcome decline in PCPC from baseline to ICU discharge with 95% C.I. for REDvent vs. usual care will be presented.	April 2024- Evaluated possibility of using continuous variable but was highly skewed with little variability so it was dichotomized.
Decline in POPC from baseline to ICU discharge	Change in POPC defined as baseline minus ICU discharge value. This change was dichotomized into a change of ≥ 0 (no change or increased) vs. change of <0 (decline in POPC).	Patients who did not survive to ICU discharge were excluded.	Multiple logistic regression controlling for blocking variables and confounders.	Adjusted odds ratio for the outcome decline in POPC from baseline to ICU discharge with 95% C.I. for REDvent vs. usual care will be presented.	April 2024- Evaluated possibility of using continuous variable but was highly skewed with little variability so it was dichotomized.
Improvement in FSS from baseline to ICU discharge	Change in FSS defined as baseline minus ICU discharge value. This change was grouped into ordinal categories: no change/improvement (change of ≥ 0), 1-2 point decline, and >2 point decline.	Patients who did not survive to ICU discharge were excluded.	Proportional odds logistic regression controlling for blocking variables and confounders. Ordered on the probability towards improvement.	Adjusted odds for the improvement (change going towards positive) with 95% C.I. for REDvent vs. usual care.	April 2024- Evaluated possibility of using continuous variable but was highly skewed with little variability so it was grouped into categories.
Decline in PCPC from baseline to hospital discharge	Change in PCPC defined as baseline minus hospital discharge value. This change was dichotomized into a change of ≥ 0 (no change or increased) vs. change of <0 (decline in PCPC).	Patients who did not survive to hospital discharge (censored at 90 days) discharge were excluded.	Multiple logistic regression controlling for blocking variables and confounders.	Adjusted odds ratio for the outcome decline in PCPC from baseline to hospital discharge with 95% C.I. for REDvent vs. usual care will be presented.	April 2024- Evaluated possibility of using continuous variable but was highly skewed with little variability so it was dichotomized.

Decline in POPC from baseline to hospital discharge	Change in POPC defined as baseline minus hospital discharge value. This change was dichotomized into a change of ≥ 0 (no change or increased) vs. change of < 0 (decline in POPC).	Patients who did not survive to hospital discharge (censored at 90 days) discharge were excluded.	Multiple logistic regression controlling for blocking variables and confounders.	Adjusted odds ratio for the outcome decline in POPC from baseline to hospital discharge with 95% C.I. for REDvent vs. usual care will be presented.	April 2024- Evaluated possibility of using continuous variable but was highly skewed with little variability so it was dichotomized.
Improvement in FSS from baseline to hospital discharge	Change in FSS defined as baseline minus hospital discharge value. This change was grouped into ordinal categories: no change/improvement (change of ≥ 0), 1-2 point decline, and > 2 point decline.	Patients who did not survive to hospital discharge (censored at 90 days) discharge were excluded.	Proportional odds logistic regression controlling for blocking variables and confounders. Ordered on the probability towards improvement.	Adjusted odds for the improvement in FSS (change going towards positive) with 95% C.I. for REDvent vs. usual care.	April 2024- Evaluated possibility of using continuous variable but was highly skewed with little variability so it was grouped into categories.

Table 2: Outcome variables, modelling approaches, and interpretation of models

Model Name	Outcomes	Methods	Interpretation
Negative Binomial Model	Length of Weaning (initial plan- revised); Ventilator Free Days	Count variables with adjustment for blocking variables and confounders. Model assumptions and methods to evaluate model fit: Pearson Chi-square/deviance for over and under-dispersion, DFBETAS and variance inflation factor.	Raw estimate and 95% C.I. for REDvent vs. usual care exponentiated to obtain Incidence Rate Ratio with 95% C.I. Patients in the REDvent group had a decreased rate of length of weaning by x% compared to usual care after adjusting for blocking variables and confounders.
Logistic regression	First SBT success; re-intubation, NIV/NRS use post extubation; ICU and 90 day mortality; decline in PCPC or POPC;	Binary outcomes with adjustment for blocking variables and confounders. Firth's penalized likelihood method was used in subgroup analyses when event rates were small to reduce bias in the parameter estimates.	Odds Ratio with 95% C.I. Patients in the REDvent group had higher odds (if OR>1) of achieving the outcome than usual care after adjustment for blocking and confounding variables.
Linear Regression	Days to first SBT and SBT passage; length of IMV; length of NRS/NIV post extubation; ICU Length of Stay; Hospital Length of Stay	Continuous outcomes with adjustment for blocking variables and confounders. Residuals evaluated for normality, homoscedasticity. DFBETAS and variance inflation factors assessed for influence of observations. Log transformation of the outcome used when appropriate.	Relative change (slope) of regression coefficient with 95% confidence interval. Patients in the REDvent group had a reduction in length of IMV by x compared to usual care. If log transformation used the estimate for the adjusted mean difference and 95% C.I. on the log scale were exponentiated. Outcome decreased by x% in the REDvent group compared to usual care.
Proportional Odds Logistic Regression	Length of weaning, PiMax variables, Functional Status Scale	Proportional odds assumption checked for each covariate with empirical cumulative logit figures for parallel slopes, also overall using the score Chi-square test (null hypothesis is that there is no evidence of non-proportional odds).	Odds were ordered appropriately depending on the outcome (length of weaning= odds lower length of weaning, PiMax= odds of higher PiMax, FSS= odds of higher change in PiMax). The odds of decreased length of weaning in the REDvent group vs. usual care, while controlling for blocking variables and confounders.

Summary of Changes and timeline for REDvent SAP.

Full details are provided in the final SAP with the rationale for changes in the text, and a summary of the changes in the table.

Date	Summary of changes
November 2017	Initial protocol approved and enrollment began. Basic SAP detailed in initial study protocol, with ongoing work with statistical team to develop each outcome and analytic approach in fully detailed SAP.
Fall 2019	Full detailed SAP developed with definitions for all outcome variables and detailed analytic plan for each outcome variable.
October 2019	Target Sample size reduced from 300 to 276 based on number of patients meeting primary outcome
January 2023	Analytic plan for primary outcome variable changed to align with count like distribution of data. Power analysis reconsidered, minimum sample size revised to 230, with target between 230-276.
January 2024	Mock tables finalized with all specified outcomes. Added use of NIV and NRS as count variables in addition to the duration variables to aid interpretation of duration.
April/May 2024	Primary outcome found to be highly influenced by few observations with count-model approach (negative binomial). Revised to proportional odds approach. Consideration of modeling FSS/POPC/PCPC as continuous but data too sparse and stuck with ordinal/dichotomous.
June 2024	PiMax variables did not satisfy assumptions of linear regression with transformation- changed to proportional odds regression. Clarification and articulation of methods used to assess for co-linearity, assessment of model assumptions, and interpretation of output of each of the models.

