Duration of invasive ventilation is the number of days and hours that the patient is intubated (from insertion to removal), censored 60 days after study enrollment. For calculations, removal of the ETT will be calculated as the first time the tube is continuously absent for at least 24 hours. For tracheostomy patients, the end of intubation is defined as removal of positive pressure mechanical ventilation without re-initiation for at least 24 hours. Re-intubation after 24 hours and subsequent periods of invasive mechanical ventilation within 60 days of study enrollment will be summed together to represent total duration of IMV.

3. **Duration of Non-Invasive Mechanical Ventilation (NIV) after extubation– Secondary Outcome**
Duration of non-invasive ventilation after extubation is defined as the number of days and hours that the patient is on oro-nasal mask CPAP with minimal pressure of 5 cmH₂O, or Bi-Level ventilation (at any pressure) after extubation, censored 60 days after study enrollment. For calculations, the end of Non-Invasive Ventilation will be calculated as oro-nasal mask CPAP (minimal 5 cmH₂O) or BIPAP as continuously absent for at least 24 hours. Resumption of NIV after 24 hours and subsequent periods of non- invasive mechanical ventilation within 60 days of study enrollment will be summed together to represent total duration of NIV after extubation.

4. **Duration of Non-Invasive Mechanical Ventilation (NIV) before intubation– Secondary Outcome**
Duration of non-invasive ventilation before intubation is defined as the number of days and hours that the patient is on oro-nasal mask CPAP with minimal

pressure of 5 cmH₂O, or Bi-Level ventilation (at any pressure) prior to intubation. This is necessary to correctly compute ventilator free days. For calculations, the patient must have been on Non-Invasive Ventilation in the 24 hours prior to intubation.

5. Duration of Non-Invasive Respiratory Support (NRS) after extubation- Secondary Outcome

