Non-invasive respiratory support includes: High Flow Nasal Cannula (HFNC) or nasal-only modes of non-invasive ventilation (CPAP or Nasal IMV or BiPAP). It does not include oxygen therapy via face mask, nasal cannula, oxygen hood, or blow by oxygen alone. Duration of NRS after extubation is defined as the number of days and hours that the patient is on NRS after extubation, censored at 60 days after study enrollment. For calculations, the end of NRS will be calculated as NRS being continuously absent for at least 24 hours. Resumption of NRS after 24 hours and subsequent periods of NRS within 60 days of study enrollment will be summed together to represent total duration of NRS after extubation.

6. Re-intubation within 48 hours of extubation- Secondary Outcome

Re-intubation will be defined as re-insertion of the endotracheal tube within 48 hours of the initial extubation. For tracheostomy patients, re-intubation is defined as re-initiation of positive pressure mechanical ventilation within 48 hours of discontinuation.

7. Re-intubation within 7 days of extubation- Secondary Outcome

Re-intubation will be defined as re-insertion of the endotracheal tube within 7 days of the initial extubation. For tracheostomy patients, re-intubation is defined as re-initiation of positive pressure mechanical ventilation within 7 days of discontinuation.

8. Ventilator Free Days- Secondary Outcome

Because the acute phase of ventilation is often long and less predictable, weaning duration was chosen as the primary outcome because there is more variability in Ventilator Free Days (VFDs) than in weaning duration. However VFDs is a secondary outcome. VFDs will be calculated at 28 and 60 days, defined as total number of days after initiation of MV in which the patient is alive and not on ventilation. The components of length of mechanical ventilation used for VFD calculations include length of IMV (2 above), length of NIV after extubation (3 above) and length of NIV prior to intubation (4) above. Patients who die within the 28 or 60 days will have 0 28 or 60 Day VFDs respectively.

9. Use and duration of rescue therapies - Secondary Outcomes

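### The SAP ends invasive-ventilation duration at the first extubation that lasts 24 hours, while the protocol adds later re-intubations, so one outcome name covers two different quantities

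*Combined protocol and SAP*

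**What the plan says.** **SAP.** In Table 1 of both the Fall 2019 SAP and the final SAP (July 2024), the row for IMV duration in survivors is defined as "Time from start of index intubation to successful liberation. Successful liberation is defined as no death or re-intubation within 24 hours of extubation". Neither row says what happens to ventilation after that point. The only death exclusion stated is death within 24 hours of extubation. The final SAP adds "Patients who are intubated past 90 days of index intubation are imputed as 90 days". That rule is not in the Fall 2019 row, yet the change column for this row reads None. Table 2 of the final SAP interprets the result as a reduction in length of IMV.

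**Protocol.** C.3.1 item 2, in both protocol versions, uses 24 hours to close one period: "removal of the ETT will be calculated as the first time the tube is continuously absent for at least 24 hours". It then continues: "Re-intubation after 24 hours and subsequent periods of invasive mechanical ventilation within 60 days of study enrollment will be summed together". The duration is "censored 60 days after study enrollment".

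**Neighbouring outcomes.** The SAP row for 28-day ventilator-free days deals with later re-intubation explicitly: "If a patient is extubated for >24 hours and then subsequently re-intubated they get credit for those days without IMV". Re-intubation is a separate SAP outcome, "Binary variable for re-insertion of endotracheal tube within 48 hours of initial extubation", in line with protocol C.3.1 item 6.

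**The concern.** The protocol's outcome is total time on invasive ventilation. The SAP's variable is time to the first liberation that holds for 24 hours. The two agree for a child who is never re-intubated more than 24 hours after extubation (and not still intubated at the horizon), and differ for every child who is.

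The trial's central hypothesis is less time on ventilation, and clinicians are not blinded. If one arm had more extubations that failed after the first day, the SAP variable would leave out the ventilation those failures caused. A reader of the results, told that this is length of IMV, would not know that it had been left out.

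**Working it through.** The documents give no sample size, power or expected value for this outcome, so there is no plan figure to reproduce. The check compares the definitions and then illustrates scale.

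**1. One child under both definitions (assumed course).** Intubated 5 days, extubated 30 hours, re-intubated for 10 days, all within 60 days of enrollment.
- SAP: the extubation lasted more than 24 hours, so the clock stops at 5 days.
- Protocol: 5 + 10 = 15 days.
- SAP 48-hour re-intubation outcome: 30 hours is less than 48, so this child is an event.

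The child is therefore a successful liberation in one row and a re-intubation in another. A re-intubation within 24 hours does not stop the SAP clock and causes no discrepancy.

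**2. Horizon.** The protocol stops at 60 days from enrollment, the final SAP at 90 days from index intubation. With enrollment up to 72 hours after intubation, a continuously ventilated child can reach at most 60 + 3 = 63 days under the protocol, but is given 90 under the SAP. Here the SAP value is the longer one, by at least 90 − 63 = 27 days. This is not hypothetical: the final SAP's May 2024 note describes two usual-care children still on IMV at 90 days.

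**3. Survivors.** Take a child liberated for 25 hours, then re-intubated, who later dies. The row's title suggests exclusion; its stated exclusion rule does not remove the child. The row does not settle the question.

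**4. Scale at arm level.** The analysis is log-linear, so the relevant quantity is the geometric mean.

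Inputs:
- First episode B = 6.5 days, the pilot REDvent median length of ventilation (protocol Table 1), used only as a scale.
- Further IMV days E = 5 to 10: an assumption.
- Difference d between arms in the share re-intubated after 24 hours, 0.05 or 0.10: an assumption. For context, the protocol expects 10% re-intubation without giving a window, and its earlier cohort had 34/409 = 8.3% within 48 hours; neither figure isolates events after 24 hours.

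Formula: log shift x = d × ln((B + E)/B). The SAP understates the arm with more late re-intubation, relative to the other, by 1 − exp(−x).

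ln(11.5/6.5) = 0.5705 and ln(16.5/6.5) = 0.9316.

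| d | E (days) | x | 1 − exp(−x) |
|---|---|---|---|
| 0.05 | 5 | 0.0285 | 2.8% |
| 0.05 | 10 | 0.0466 | 4.6% |
| 0.10 | 5 | 0.0571 | 5.5% |
| 0.10 | 10 | 0.0932 | 8.9% |

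Seen from the other arm, the same shifts are exp(x) − 1 = 2.9%, 4.8%, 5.9% and 9.8%. With d = 0 the between-arm ratio does not move, although both arms' durations are still understated.

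**The case against.** The strongest defence has four parts.

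**The estimand is legitimate.** Time to a first liberation that lasts 24 hours is a sensible quantity, and 24 hours is the protocol's own threshold for tube removal and for successful extubation in the primary outcome. This stands, but it supports relabelling the variable, not giving it the name of the protocol's total.

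**Other outcomes would show the problem.** Ventilator-free days lose the later IMV days, and 48-hour re-intubation is reported. SA1 names ventilator-free days and extubation failure as its secondary outcomes, and IMV duration is not in the protocol summary's endpoint list. This largely stands and confines the point to one lower-tier outcome. The cover is partial: the protocol's 7-day re-intubation and 60-day ventilator-free days have no row in either SAP's Table 1, so ventilation after a re-intubation beyond 48 hours is counted directly only in ventilator-free days, and only to day 28.

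**The direction is unknown.** Both arms use the same breathing-trial and extubation-readiness criteria, and the protocol expects preserved muscle strength to reduce re-intubation. If so, the SAP variable would understate a REDvent benefit. This stands: a reader might infer a bias towards REDvent, but the documents do not support either direction.

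**A recode now comes after unblinding.** The final SAP records that the unblinded statistician was already analysing in May 2024. This stands, and is why both versions should be shown.

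The final SAP also refers to a published protocol for further detail. That paper is not available here, and the row as written has no rule for later periods.

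**Conclusion.** The contradiction is real and needs no assumptions: followed as written, the SAP does not produce the outcome in protocol C.3.1 item 2. The rule for later periods is absent, the horizon is different, and survivor is undefined beyond the 24-hour exclusion. For an affected child the gap can be large (5 days against 15 in the example).

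The effect on the comparison between arms cannot be found from the documents. Under the assumed values it is about 3–5% for a 5-point difference in re-intubation after 24 hours and about 6–9% for a 10-point difference, in either direction, and nil if the rates are equal. Ten points is also the full non-inferiority margin the protocol sets for re-intubation overall, so the upper range is an extreme case.

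Three stronger readings should be resisted.
- **A late change to the liberation definition.** Its wording is identical in Fall 2019.
- **A concealed departure from the protocol.** The change column tracks changes to the SAP's own approach, so None is correct for the definition and wrong only for the added 90-day imputation. The documents do not date that addition, so they do not show that it followed sight of the data.
- **Later deaths certainly counted as short durations.** The row is ambiguous on this and shows no more than that.

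**What to change.** 1. Report total IMV by the protocol's definition, adding all invasive periods within 60 days of enrollment, and define survivor as alive at that horizon.
2. Report the present SAP variable beside it, renamed as time to first liberation sustained for 24 hours.
3. Record in the change log, with dates, the departure from the protocol's summing rule and the added 90-day imputation, and state that the correction was made after unblinding.

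The cost is SAP wording and one recoded variable, using intubation dates that the protocol's definition already requires. The downsides are slightly more skew in the summed outcome and one additional reported variable. No new data collection is needed.

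### NIV and NRS duration after extubation are compared between arms only among children who received that support, so the reported percentage change is not a randomised comparison and can point the wrong way if REDvent mainly averts short courses

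*Combined protocol and SAP*

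**What the plan says.** Table 1 of the final SAP (July 2024) restricts the NIV duration row with "Patients who die within 24 hours of IMV or who never receive NIV post-extubation are excluded" and the NRS duration row with "Patients who die within 24 hours of IMV or who never receive NRS post-extubation are excluded". For deaths on support the NIV row says "Patients who die while on NIV will have their death date as end of NIV duration". The NRS row says "Patients who die while on NRS will have their death date as end of NIV duration", where NIV is presumably a slip for NRS. The planned model in both rows is "Log transformed multiple linear regression controlling for blocking variables and confounders". The coefficient is exponentiated and read as a relative change, with a 95% CI. Table 2 gives the template for logged outcomes, "Outcome decreased by x% in the REDvent group compared to usual care", with nothing to limit it to recipients.

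The final SAP also has two yes/no outcomes, receipt of NIV and receipt of NRS, analysed by logistic regression. Their set is successfully extubated children, leaving out those who die within 24 hours of IMV or are still on IMV at 90 days. The note on the NIV row reads "January 2024 added as necessary component to interpret length of NIV after extubation more appropriately", and the NRS row carries a matching note.

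Protocol section C.3.1, item 3, gives the underlying definition: "Duration of non-invasive ventilation after extubation is defined as the number of days and hours that the patient is on oro-nasal mask CPAP", or on bi-level ventilation. It does not say how a child who never used NIV is handled. The Fall 2019 SAP already had the recipients-only rule and the death rule, without the yes/no rows.

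**The concern.** Randomisation makes the arms comparable as randomised. It does not make the children who go on to need NIV or NRS comparable, because the intervention may change who needs it. The SAP accepts this possibility by comparing receipt between arms. Baseline covariates in the model do not restore comparability within a subset selected after randomisation.

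The risk has a direction. REDvent aims to preserve respiratory muscle strength. If that spares children with mild, brief needs, those short courses leave the REDvent recipients but stay in the usual-care recipients. The average among recipients then rises in the REDvent arm although no child was supported for longer.

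No other listed outcome supplies the missing answer. The protocol's ventilator-free days count NIV after extubation for all patients, but the final SAP's version counts only days alive and off IMV, and NRS is in neither. Total NIV or NRS burden across extubated children is therefore not analysed.

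The death rule is a separate matter. A child who dies on support gets a shorter recorded duration, whereas in the protocol's ventilator-free days a death scores zero.

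**Working it through.** There is no figure in the plan to reproduce: neither the protocol nor the SAP gives a use rate, mean, SD or power for these durations. The check shows the mechanism and a range on assumed inputs.

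**A small exact example.** Take 100 extubated children per arm.
- Usual care: 40 children with no NIV, and 20 each with 1, 3 and 6 days.
- REDvent: the same, except that the 20 one-day courses are avoided.
- Planned contrast (recipients, log scale): geometric mean (1×3×6)^(1/3) = 2.62 days in usual care and (3×6)^(1/2) = 4.24 days in REDvent. The ratio is 4.24/2.62 = 1.62, read as 62% longer.
- All children, non-users at 0: (20+60+120)/100 = 2.0 days against (60+120)/100 = 1.8 days. The ratio is 0.90.

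**A range.** Assumptions: 40% use in usual care, lognormal duration with median 2 days and log-SD 1, one third of REDvent courses averted and the rest unchanged, 100 extubated children per arm. Mean NIV per child in usual care is 0.40 × 2 × exp(1²/2) = 1.32 days. Only the choice of averted courses varies:

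| Courses averted | Recipients-only ratio | Mean days per child, REDvent | Significantly longer |
|---|---|---|---|
| At random | exp(0) = 1.00 | 1.32 × 2/3 = 0.88 | about 3% of trials |
| Chance falls linearly with duration rank | exp[1/(2√π)] = 1.33 | 1.32 × 0.840 = 1.11 | about 20% |
| Exactly the shortest third | exp[φ(−0.431)/(2/3)] = 1.73 | 1.32 × 0.924 = 1.22 | about 67% |

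In the second row the retention weight at rank u is 1/3 + 2u/3, so the factor is 1/3 + (2/3)Φ(1/√2) = 0.840. In the third, it is Φ(1 + 0.431) = 0.924. The last column comes from simulated two-sided t-tests on log duration at 0.05. Mean support per child falls in every row, and the planned estimate shows that in none of them.

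**Other assumptions.** With 120 children per arm and 40% use, preventing 25% of below-median courses gives a recipients-only ratio of 1.07 to 1.12 for log-SD 0.6 to 1.0 (about 8% significantly longer). Preventing 50% gives 1.17 to 1.30 (about 23%). The all-child mean ratio is 0.93 to 0.96 and 0.86 to 0.92 respectively.

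**The death rule alone.** If a fraction k of an arm's recipients die at a fraction f of what would have been their course, the geometric mean is multiplied by f^k. For k = 5% and f = 0.5 this is 0.966; for k = 10% and f = 0.25 it is 0.871. Deaths shorten the arm's estimate, the opposite direction from averted short courses in the same arm.

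**The case against.** The best defence is that the SAP saw the problem and answered it in January 2024. Use and duration-if-used then stand side by side as a two-part presentation, and each use row gives an adjusted odds ratio with a 95% CI. A reader who sees fewer REDvent children on NIV beside a longer duration can work out why. In the shortest-third scenario the use comparison detects fewer REDvent users in 51% of simulated trials, against 30% for an all-child rank test. This stands as mitigation. It does not turn the duration estimate into a treatment effect, and it gives no result for total burden.

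The size is also open. A reversal needs averting to favour short courses. If REDvent instead lowered need uniformly, so that every course shrank and the mildest vanished, one such model gives a recipients-only ratio of 0.83, the correct sign. That stands too, and is why a range is given.

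Three stronger readings are tempting but unsupported:
- A child placed on NIV at extubation who dies the same day might seem to count as a favourable short course. That child is excluded, because successful extubation requires survival for 24 hours. Only a later death on support can enter.
- The SAP might seem to contradict a protocol rule scoring non-users as 0 days. The protocol is silent on non-users. Its ventilator-free-day definition fits a zero but does not state one for this outcome.
- The restriction might look like a late change. It was already in the Fall 2019 SAP.

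**Conclusion.** The point holds. Followed as written, the final SAP produces for both durations an adjusted relative change with a 95% CI that is conditional on a post-randomisation event, under a Table 2 template that does not say so. Covariate adjustment and the yes/no rows do not remove that conditioning.

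On the stated assumptions the apparent effect runs from none (ratio 1.00) to about 70% longer (ratio about 1.7), while mean support per child falls throughout. A reader might infer that the trial's NIV or NRS result will have the wrong sign. The documents do not support that: the upper end assumes that exactly the shortest third is averted and nothing else changes, and the plan gives no data to say which pattern applies.

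The death rule is a lesser, separate defect. Deaths within 24 hours of extubation are already out, the protocol expects up to 12% mortality before the first SBT, and ICU and 90-day mortality are analysed without exclusions. The effect is therefore likely to be small, although the number of later deaths on support is not given.

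These are secondary outcomes with no power claim, and the primary outcome is unaffected. The change should be made, but the trial's main conclusion does not depend on it.

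**What to change.** 1. In Tables 1 and 2, label the NIV and NRS duration outcomes as among recipients. Report medians by arm as description, without a treatment-effect estimate or CI.
2. Add, for each type of support, an analysis of all children in the matching yes/no-use set: 0 days for non-users, and death on support ranked worst. Use the ungrouped proportional-odds model that the SAP already applies to PiMax, with the same blocking variables and confounders.
3. Date this as a post-hoc change, since data collection was complete and the statistician unblinded by May 2024.
4. State that deaths on IMV or within 24 hours of extubation, and children still on IMV at 90 days, fall outside this set, which is itself defined after randomisation. As a sensitivity analysis, rank all deaths and all children still on IMV as worst, so that every randomised child is included and deaths are treated alike.
5. Correct the NRS row's reference to NIV duration.

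The cost is wording in two outcome rows and a re-run on data in hand. The drawback is that an odds ratio is less directly interpretable than a percentage change in days; median days per child by arm, zeros included, can be shown beside it.
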